### 9.6.7 Additional Therapy

Some subjects may receive additional therapies with AU-011 or standard care after Visit 11 (Week 12) if the Investigator determines that ocular melanoma has progressed and further treatment (additional therapy) is required. Number and percentage of those subjects who receive AU-011 will be summarized by original cohorts and overall. The highest established safe dose and regimen of drug and laser that was given at the time of the request will also be present.

Number and percentage of subjects receiving additional therapy other than AU-011 will be summarized by cohort and overall for the safety population. Details of the treatment administration for each individual subject will be provided in a data listing.

## 10 Interim Analysis

Two interim analyses were planned to summarize the safety and efficacy results of AU-011 as mentioned in Section 4.2.

One interim analysis was performed for the '01AUG2018 Deliverable'. It has been decided that no additional interim analysis will be performed.

## 11 Appendices

### 11.1 Schedule of Assessments

Assessment	Screening	Active Period							Follow-up Period							End of Study or Early Termination
	Visit 1 D-28 to 1	Visit 2 D1	Visit 3 D2 ± 4H	Visit 4 D8 + 1D	Visit 5 D9 ± 4H	Visit 6 a D15 + 1D	Visit 7 D16 ± 4H	Visit 8 D29± 1D	Visit 9 W6 ± 3D	Visit 10 W8 ± 3D	Visit 11 W12 ± 3D	Visit 12 W26 ± 7D	Visit 13 W39 ± 7D	Visit 14 W52 ± 7D	Visit 15 W78 ± 7D	Visit 16 W104 ± 7D or Early Termination
Informed consent	X															
Eligibility review	X	X														
Demographics	X															
Medical and ophthalmic history	X															
Vital signsa	X	X	X	X	X j	X	X k	X					X		X	
Pregnancy test	X	X b														
Laboratory assessments (CBC with differential and CMP)	X c	X c		X c				X c								
Light-activated AU-011 treatment		X d		X j		X k										
ADA samples	X			X		X k		X			X			X		
BCVA	X	X e	X	X	X j	X	X k	X	X	X	X	X	X	X	X	
Slit lamp biomicroscopyf	X	X	X	X	X j	X	X k	X	X	X	X	X	X	X	X	
IOPf	X	X	X	X	X j	X	X k	X	X	X	X	X	X	X	X	
Fundoscopyf	X	X	X	X	X j	X	X k	X	X	X	X	X	X	X	X	
Fundus photosf	X	X e	X	X	X j	X	X k	X	X	X	X	X	X	X	X	
FAf	X										X		X		X	
EDI-OCTf	X	X e	X	X	X j	X	X k	X	X	X	X	X	X	X	X	
OCTAf,p	X	X e	X	X	X j	X	X k	X	X	X	X	X	X	X	X	
B-scanf	X	X e	X i	X		X		X		X	X	X	X	X	X	
A-scan (study eye only)	X			X				X		X	X	X	X	X	X	
Visual field examf	X										X		X		X	
AE reviewg	X g	X	X	X	X j	X	X k	X	X m	X n	X h,q	X h,q	X h,q	X h,q	X h,i,q	
Concomitant medication reviewg	X	X	X	X	X j	X	X k	X	X j	X k	X q	X q	X q	X q	X g,q	

Confidential

aVital signs include BP seated and pulse.

bSerum pregnancy test will be performed at Visit 1. If Visit 2 occurs more than 7 days after Visit 1, then urine pregnancy test will be performed at Visit 2.

cCBC with differential includes hemoglobin, hematocrit, red blood cells (RBC), white blood cells (WBC), WBC differential, and platelets. CMP includes total bilirubin, direct bilirubin, alkaline phosphatase, ALT (SGPT), AST (SGOT), GGT, LDH, blood urea nitrogen (BUN), creatinine, glucose, uric acid, calcium, phosphorus (or phosphate), total protein, albumin, globulin, triglycerides, cholesterol, CK, sodium, potassium, bicarbonate, chloride, and magnesium. If Visit 2 occurs more than 7 days after Visit 1, then laboratory assessments will be repeated at Visit 2.

dSubjects should remain at the study site following intravitreal injection until approximately ½ hour after laser treatment. If subjects are discharged during daylight hours, appropriate sun protection, e.g., sunglasses and a hat, will be required.

eIf Visit 1 and Visit 2 are within 7 days, the following procedures do not need to be repeated prior to AU-011 study drug injection, unless clinically indicated: BCVA, fundus photos, EDI-OCT, OCTA, and B-scan.

fFA and Fundus photos, EDI-OCT, OCTA, B-scan, Visual Field, IOP, Slit lamp and Fundoscopy will be performed in both eyes at Visit 1 (Screening) and Visit 11 (Week 12), and at any Early Termination Visit if that occurs before Visit 11 (Week 12), and in the study eye only at all remaining visits where applicable for each assessment.

gIf Early Termination Visit occurs ≤ 30 days following study treatment.

hStudy product and/or study procedure related AEs only for Cohorts 1 to 9.

iAny AE for up to 30 days after the last AU-011 treatment if Early Termination Visit occurs ≤ 30 days following study treatment.

jFor 2 and 3 Repeat Light-activated AU-011 administration cohort subjects only

kFor 3 Repeat Light-activated AU-011 administration cohort subjects only

lFor Cohort 1, 2 and 3 subjects only

mFor Single Light-activated AU-011 administration cohort subjects, only study product and/or study procedure related AEs. For 2 and 3 Repeat Light-activated AU-011 administration cohort subjects, any AE.

nFor Single Light-activated AU-011 administration cohort and 2 Repeat Light-activated AU-011 administration cohort subjects, only study product and/or study procedure related AEs. For 3 Repeat Light-activated AU-011 administration cohort subjects, any AE.

oFor the observation cohort (Cohort 10) every 3 month visits (i.e. 90 day (+/- 7 days) intervals from the Screening Visit) prior to evidence of tumor growth, all procedures outlined for Visit 6 (Day 15) will be performed with the exception of OCTA and Anti-drug Antibody (ADA) testing which is not required.

pFor Cohort 6, 7, 8, and 9 subjects only

qFor Cohort 10, 11, and 12 subjects, all SAEs and AEs and concomitant medications will be reported from the time the subject signs the informed consent through their last study visit.

## 11.2 Definition of Visit Windows in Reporting

The definition of visit label and visit windows in reporting are described in the table below.

Study Period	Visit Label	Definition [Day window]
Screening	Visit 1	= Subject screening date; nominally 1 to 28 days prior to the first AU-011 treatment. 'Day 1' - 'Date of assessment' = [1 to 28]. Alternatively, this is the assessment before the first treatment date.
Active Period	Visit 2 - D1 (Baseline)	= An assessment with the same date as recorded on the Day 1 Administration CRF Target date = 1
	Visit 3 - D2	= An assessment where 'Date of assessment' - 'Day 1' + 1 = 2 Target date = 2
	Visit 4 - D8	= An assessment where 'Date of assessment' - 'Day 1' + 1 = [8 - 9] Target date = 8
	Visit 5 - D9	= An assessment where 'Date of assessment' - 'Day 1' + 1 = [9 - 10] Target date = 9. Alternatively, this is the assessment one day after Visit 4 - D8.
	Visit 6 - D15	= An assessment where 'Date of assessment' - 'Day 1' + 1 = [15 - 16] Target date = 15
	Visit 7 - D16	= An assessment where 'Date of assessment' - 'Day 1' + 1 = [15 - 17] Target date = 16. Alternatively, this is the assessment one day after Visit 6 - D15.
Follow-up Period	Visit 8 - D29	= An assessment where 'Date of assessment' - 'Day 1' + 1 = [22 - 36] Target date = 29
	Visit 9 - W6	= An assessment where 'Date of assessment' - 'Day 1' + 1 = [37 - 50] Target date = 43
	Visit 10 - W8	= An assessment where 'Date of assessment' - 'Day 1' + 1 = [51 - 64] Target date = 57
	Visit 11 - W12	= An assessment where 'Date of assessment' - 'Day 1' + 1 = [65 - 113] Target date = 85
	Visit 12 - W26	= An assessment where 'Date of assessment' - 'Day 1' + 1 = [155 - 211] Target date = 183
	Visit 13 - W39	= An assessment where 'Date of assessment' - 'Day 1' + 1 = [246 - 302] Target date = 274
	Visit 14 - W52	= An assessment where 'Date of assessment' - 'Day 1' + 1 = [337 - 393] Target date = 365
End of Study	Visit 15 - W78	= An assessment where 'Date of assessment' - 'Day 1' + 1 = [463 - 631] Target date = 547
	Visit 16 - W104	= An assessment where 'Date of assessment' - 'Day 1' + 1 = [700 - 756] Target date = 728

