10.1.7. Visit 6 (Day 15 to Day 16)

During this Visit, the following procedures will be performed:

- Vital Signs
- BCVA (Both Eyes)
- Slit lamp biomicroscopy
- IOP
- Fundoscopy
- Fundus photos
- EDI-OCT

- OCTA (Cohorts 6 to 9 only)
- B-scan
- Blood sample for ADA testing (Performed pre-dose and required for 3 repeat Lightactivated AU-011 administration cohort subjects only)
- Record AEs
- Record concomitant medications

FOR 3 REPEAT LIGHT-ACTIVATED AU-011 ADMINISTRATION COHORTS ONLY:

- Administration of Light-activated AU-011 treatment
 - Intravitreal injection of AU-011 study drug (Subjects in cohorts 7, 8, 9, 10 [after observation of growth], 11 and 12 receiving 80 μg doses administered as 2 injections of 40 μg in μl given as μl injections will have their IOP measured prior to and after each injection. IOP must be 21 mm Hg or less before each injection can be given and the maximum interval between the two injections is 2 hours. IOP must also be 21 mm Hg or less before the patient is discharged from the clinic).
 - Laser treatment (single laser applications for cohorts 5 and 7, and two laser applications for cohorts 8, 9, 10 [after observation of growth], 11 and 12 given 6 to 8 hours after intravitreal administration of AU-011). For subjects in cohorts 7, 8, 9, 10 [after observation of growth], 11 and 12 receiving 80 μg doses administered as 2 injections of 40 μg in μl, laser treatment is 6 to 8 hours after the second injection. If the fovea near the tumor edge, an adjustment to the laser procedure should be performed as outlined in section 8.2.2 and the Injection and Laser Procedure Manual. Subjects should remain at the study site after intravitreal injection until approximately ½ hour after laser treatment.
 - If subjects are discharged during daylight hours, appropriate sun protection, e.g., sunglasses and a hat, will be required.
 - Subjects must return to the study site for additional assessments 24 hours (± 4 hours) after AU-011 intravitreal administration, refer to Section 10.1.4.

10.1.8. Visit 7 (Day 16 to Day 17, 24 hours [± 4 hours] Post-Injection Follow-up for 3 Repeat Light-activated AU-011 Administration Cohorts only)

Twenty-four hours (\pm 4 hours) following intravitreal administration of AU-011 study drug, subjects are required to return to the study site for the following assessments:

- Vital signs
- BCVA (Both Eyes)
- Slit lamp biomicroscopy
- IOP

- Fundoscopy
- Fundus photos
- EDI-OCT
- OCTA (Cohorts 6 through 9 only)

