#### 4.1.2 Visit Windows

The schedule of study assessments can be found in Appendix 11.1 of this SAP.

Missing scheduled visit will be substituted by an unscheduled or early withdrawal visit occurring within each follow-up visit window. If there are multiple unscheduled or early withdrawal visits occurring within the window, the closest one within the visit window will be used. If no unscheduled or early withdrawal visit occurred within the window, the visit will be considered as missing. The details are tabulated in Appendix 11.2.

An exception to this visit-window algorithm is the analysis of the "Last Visit". For all "Last Visit" time-point analyses, a subject's last non-missing endpoint assessment will be used for the analysis, regardless of if the visit falls within a particular visit window or not.

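### SAP 11.2 opens the Visit 7 window on the Day 15 dosing day and gives no precedence to its own one-day-after rule, so a pre-injection exam can meet the definition of a 24-hour post-injection visit

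*SAP*

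**What the plan says.** SAP 11.2 states that it defines the visit labels and windows used in reporting. Each row is built on the date of assessment counted from Day 1. The four rows at issue are:

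- Visit 4, second dosing visit: "8 - 9] Target date = 8".
- Visit 5, 24 hours after the second dose: "9 - 10] Target date = 9. Alternatively, this is the assessment one day after Visit 4 - D8".
- Visit 6, third dosing visit: "15 - 16] Target date = 15".
- Visit 7, 24 hours after the third dose: "15 - 17] Target date = 16. Alternatively, this is the assessment one day after Visit 6 - D15".

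The table does not say which of the two definitions for Visits 5 and 7 comes first. It carries no dosing condition and does not say that one exam may fill only one visit.

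Protocol 10.1.7 is headed "Visit 6 (Day 15 to Day 16" and the next section, 10.1.8, "Visit 7 (Day 16 to Day 17, 24 hours [± 4 hours] Post-Injection Follow-up for 3 Repeat". SAP 11.1, footnotes j and k, limits Visit 5 to the 2- and 3-repeat cohorts and Visit 7 to the 3-repeat cohorts.

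Three other SAP rules bear on the point. Section 4.1.2 fills a missing scheduled visit from an unscheduled or early withdrawal visit in the window; where several such visits qualify, "the closest one within the visit window will be used". Section 4.6 treats assessments on a treatment day as pre-dose unless specified otherwise. Section 9.6.4 uses only the first post-baseline IOP value at each visit.

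**The concern.** Visits 5 and 7 exist to show the eye one day after a repeat injection and laser application. A window that takes in the dosing day lets an exam done before that injection count as the 24-hour exam. Safety is the primary objective, and the rows concerned include IOP, anterior chamber cells, vitreous haze and visual acuity in the repeat-dose regimens. A pre-injection value in such a row says nothing about the injection it is meant to follow.

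Two programmers could also follow this SAP faithfully and produce different Day 9 and Day 16 rows. One would label by date, the other by the nominal visit or the one-day-after clause.

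**Working it through.** **Inputs.** SAP 11.2 windows: Visit 4 Days 8–9, Visit 5 Days 9–10, Visit 6 Days 15–16, Visit 7 Days 15–17. Protocol 10.1.5 to 10.1.8: Visit 4 Days 8–9, Visit 5 Days 9–10, Visit 6 Days 15–16, Visit 7 Days 16–17.

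**Step 1: try to reproduce the SAP windows.** A 24-hour exam should fall in the dosing window moved on by one day.

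- Visit 5: 8 + 1 to 9 + 1 = Days 9–10. This agrees with the SAP and the protocol.
- Visit 7: 15 + 1 to 16 + 1 = Days 16–17. This agrees with the protocol but not with the SAP's Days 15–17.

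**Step 2: look for a reason for Day 15.**

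- The protocol tolerance of 4 hours allows an exam as early as 24 − 4 = 20 hours after injection. That is the same calendar day only if the injection was given before 24 − 20 = 04:00, so the tolerance does not explain it.
- Target plus or minus one day gives 16 ± 1 = Days 15–17, which matches. The same rule for Visit 5 gives 9 ± 1 = Days 8–10, which the SAP does not use.

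**Step 3: overlaps.**

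| Pair | Shared days, SAP 11.2 | Shared days, protocol |
|---|---|---|
| Visits 4 and 5 | 9 | 9 |
| Visits 6 and 7 | 15, 16 | 16 |

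Only the Day 15 overlap is specific to the SAP. The windows for Visits 8 to 16 do not overlap.

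**Step 4: label exams by date alone, as 11.2 is worded.** Each subject has a dosing-day exam and an exam the next day.

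| Dosing day | Exams inside the 24-hour window | Dosing-day exam qualifies? | First value in the window |
|---|---|---|---|
| 8 | Day 9 | No | Day 9, true 24-hour exam |
| 9 | Days 9, 10 | Yes | Day 9, dosing day |
| 15 | Days 15, 16 | Yes | Day 15, dosing day |
| 16 | Days 16, 17 | Yes | Day 16, dosing day |

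The last column matters for IOP because of the first-value rule in 9.6.4. On this reading it could select the dosing-day value even when the third dose is given on time, on Day 15.

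**Step 5: apply 4.1.2 instead.** Scheduled Visit 4 and Visit 6 exams keep their labels. What remains is an unscheduled or early withdrawal exam on Days 9–10 or 15–17 that replaces a missed Visit 5 or 7. Even that is uncertain, because 4.1.2 speaks of follow-up visit windows while 11.2 lists Visits 5 and 7 in the Active Period.

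**Step 6: test the smallest repair.** Changing Visit 7 to Days 16–17 clears the Day 15 row of the Step 4 table. The rows for dosing on Day 9 and Day 16 are unchanged. Counting one day from the recorded injection clears all of them.

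**The case against.** The strongest reply is that 4.1.2, not the table in 11.2, says how windows are used, and that it never ranks two attended scheduled exams against each other. This largely stands. A reader might infer that closeness to target makes a late-dosed subject's pre-injection exam win: for dosing on Day 16 the distances are 0 for the dosing-day exam and 1 for the true 24-hour exam. But the closest-date clause applies only among unscheduled or early withdrawal visits replacing a missed scheduled one, so the documents do not support that inference. Nor does 4.1.2 let a scheduled Visit 6 exam stand in for a missed Visit 7.

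A reader might also infer that subjects given no third dose enter the Visit 7 row. Cohorts 1 to 4 and 6 are planned at 3 each, 5 × 3 = 15 subjects. Footnotes j and k of SAP 11.1 and the protocol give these cohorts no Visit 7, so the count is not a measure of harm. The gap is only that 11.2 does not repeat the restriction.

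It is fair, too, that the one-day-after clause already points to the right exam and that most of the overlap comes from the protocol. Table 14.3.5.3 covers IOP increases on treatment days separately, and individual values are listed.

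What survives is that 11.2 claims to define the visit label, does so by date, starts Visit 7 a day too early, and leaves its two definitions unranked.

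**Conclusion.** The Day 15 start is an error against the protocol on any reading. Whether it changes a table depends on which rule the programmer follows, and the SAP does not settle that. If 11.2 assigns labels by date, dosing-day exams on Days 9, 15 and 16 meet the 24-hour definition. If 4.1.2 governs, the exposure shrinks to substitutes for missed visits.

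The reach is the descriptive by-visit rows for Visits 5 and 7: IOP, slit lamp, fundoscopy, vital signs and BCVA. Adverse event and DLT summaries do not use these windows, and no hypothesis is tested. This is a minor point.

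A reader might want to express the effect as a percentage dilution toward no change. The documents do not support one. They give no share of subjects dosed a day late. Such a formula would also assume that pre-injection exams at Visits 4 and 6 show no change from baseline, although repeat-dose subjects have by then had one or two treatments and may carry residual effects.

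**What to change.** In SAP 11.2, define Visits 5 and 7 only as the assessment one calendar day after the recorded AU-011 injection at Visit 4 or Visit 6, in subjects dosed at that visit. This keeps the SAP's own alternative clause and agrees with footnotes j and k of 11.1. Delete the fixed windows of Days 9–10 and Days 15–17. Add that an exam on a dosing day cannot be assigned to a 24-hour visit.

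The cost is two lines of SAP wording and a small programming change. No new data are needed, since the protocol already has sites record injection dates and times.

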## 11.3 List of Tables/Graphs/Listings

### 11.3.1 List of Statistical Tables

Table Number	Title
14.1.1.1	Study populations – All Screened Subjects
14.1.1.2	Subject Disposition – ITT Population
14.1.1.3	Summary of Major Protocol Deviations – ITT Population
14.1.2.1	Demographics and Baseline Characteristics – ITT Population
14.1.2.2	Baseline Tumor Characteristics – ITT Population
14.1.2.3	Baseline Visual Acuity Score (ETDRS Letters) – ITT Population
14.1.3.1	History of Primary Choroidal Melanoma – ITT Population
14.1.3.2	Ophthalmic History (Other Than Primary CM) by System Organ Class and Preferred Term – Study Eye – ITT Population
14.1.3.3	Ophthalmic History (Other Than Primary CM) by System Organ Class and Preferred Term – Fellow Eye – ITT Population
14.1.3.4	Medical History (Excluding Ophthalmic History) by System Organ Class and Preferred Term – ITT Population
14.1.4.1	Prior Medications by ATC Code 1 and ATC Code 4 – ITT Population
14.1.4.2	Concomitant Medications by ATC Code 1 and ATC Code 4 – ITT Population
14.1.4.3	Prior Procedures/Surgeries by System Organ Class and Preferred Term – ITT Population
14.1.4.4	Concomitant Procedures/Surgeries by System Organ Class and Preferred Term – ITT Population
14.2.1.1	Summary of Maximum Tumor Height (B-scan) and Change from Baseline in by Visit - Study Eye – ITT Population
14.2.1.2	Summary of Largest Basal Diameter (Fundus Photography) and Change from Baseline by Visit - Study Eye – ITT Population
14.2.1.3.1	Summary Of Tumor Response (Method 1) – Study Eye - ITT Population
14.2.1.3.2	Summary Of Tumor Response (Method 2) – Study Eye - ITT Population
14.2.1.3.3	Summary Of Tumor Response (Method 3) – Study Eye - ITT Population
14.2.1.3.4	Summary Of Overall Tumor Response (Method 1) – Study Eye - ITT Population
14.2.1.3.5	Summary Of Overall Tumor Response (Method 2) – Study Eye - ITT Population
14.2.1.3.6	Summary Of Overall Tumor Response (Method 3) – Study Eye - ITT Population
14.2.1.3.7	Summary Of Overall Tumor Response (Method 1) – Study Eye - ITT Population (Site 009 only)
14.2.1.3.8	Summary Of Overall Tumor Response (Method 2) – Study Eye - ITT Population (Site 009 only)
14.2.1.3.9	Summary Of Overall Tumor Response (Method 3) – Study Eye - ITT Population (Site 009 only)
14.2.2.1	Summary of Visual Acuity Score (ETDRS Letters) and Change from Baseline by Visit – Study Eye - ITT Population
14.2.2.2	Proportion of Subjects with 5, 10, 15 Letters Gain/Loss of Vision by Visit – Study Eye - ITT Population
14.2.2.3	Number and Percentage of Subjects with Visual Acuity Preservation – Study Eye - ITT Population
14.2.2.4	Summary of Visual Acuity Score (ETDRS Letters) and Change from Baseline by Visit – Study Eye - ITT Population (Site 009 only)
14.2.2.5	Number and Percentage of Subjects with Visual Acuity Preservation – Study Eye - ITT Population (Site 009 only)
14.2.3.1.1	Sensitivity Analysis - Summary of Maximum Tumor Height (B-scan) and Change from Baseline in by Visit - Study Eye – ITT Population excluding all Post-standard of care data
14.2.3.1.2	Sensitivity Analysis - Summary of Largest Basal Diameter (Fundus Photography) and Change from Baseline by Visit - Study Eye – ITT Population excluding all Post-standard of care data

Confidential

14.2.3.2.1	Sensitivity Analysis - Summary of Visual Acuity Score (ETDRS Letters) and Change from Baseline by Visit – Study Eye - ITT Population excluding all Post-standard of care data
14.2.3.2.2	Sensitivity Analysis - Proportion of Subjects with 5, 10, 15 Letters Gain/Loss of Vision by Visit – Study Eye - ITT Population excluding all Post-standard of care data
14.2.3.2.3	Sensitivity Analysis - Proportion of Subjects with 5, 10, 15 Letters Gain/Loss of Vision by Visit – Study Eye – Efficacy Evaluable Population
14.2.3.2.4	Sensitivity Analysis - Proportion of Subjects with 5, 10, 15 Letters Gain/Loss of Vision by Visit – Study Eye – Efficacy Evaluable Population excluding all Post-standard of care data
14.2.3.3.1	Sensitivity Analysis - Summary Of Tumor Response (Method 1) – Study Eye - EFFICACY EVALUABLE Population
14.2.3.3.2	Sensitivity Analysis - Summary Of Tumor Response (Method 2) – Study Eye - EFFICACY EVALUABLE Population
14.2.3.3.3	Sensitivity Analysis - Summary Of Tumor Response (Method 3) – Study Eye - EFFICACY EVALUABLE Population
14.2.3.3.4	Sensitivity Analysis - Summary Of Overall Tumor Response (Method 1) – Study Eye - EFFICACY EVALUABLE Population
14.2.3.3.5	Sensitivity Analysis - Summary Of Overall Tumor Response (Method 2) – Study Eye - EFFICACY EVALUABLE Population
14.2.3.3.6	Sensitivity Analysis - Summary Of Overall Tumor Response (Method 3) – Study Eye - ITT Population
14.2.4.1	Summary of Subretinal Fluid by EDI-OCT (Shift Table) – Study Eye – ITT Population
14.2.4.2	Summary Of Central Retinal Thickness By EDI-OCT – Study Eye – ITT Population
14.2.5.1	Summary of Orange Pigmentation on Tumor as Measured by Fundus Photography (Shift Table) – Study Eye – ITT Population
14.2.5.2	Summary of Tumor Melanosis as Measured by Fundus Photography (Shift Table) – Study Eye – ITT Population
14.2.5.3	Summary Of Greatest Basal Area By Fundus Photography – Study Eye – ITT Population
14.2.5.4	Summary Of Distance From Fovea By Fundus Photography – Study Eye – ITT Population
14.2.5.5	Summary Of Distance From Nerve Edge By Fundus Photography – Study Eye – ITT Population
14.2.6.1	Summary of Macular Edema Leakage by FA – Study Eye – ITT Population
14.2.6.2	Summary of Apical Sub-retinal Fluid by B-Scan – Study Eye – ITT Population
14.2.6.3	Summary of Vitreous Opacity by B-Scan – Study Eye – ITT Population
14.2.6.4	Summary Of Shape Of Tumor by B-Scan - Study Eye – ITT Population
14.2.6.5	Summary Of Foveal Avascular Zone Area by Octa - Study Eye – ITT Population
14.2.6.6	Summary of Vessel Density by OCTA – Study Eye - ITT Population
14.3.1.1	Extent of Exposure – AU-011 and Laser – SAF Population
14.3.1.2	Summary Of Additional Treatment – SAF Population
14.3.1.3	Summary of Dose Limiting Toxicities – SAF Population
14.3.2.1	Overview of Treatment-emergent Adverse Events (TEAE) – SAF Population
14.3.2.2	Treatment-Emergent Adverse Events by System Organ Class and Preferred Term – SAF Population
14.3.2.3.1	Ocular Treatment-Emergent Adverse Events by System Organ Class and Preferred Term – Study Eye – SAF Population
14.3.2.3.2-7	Related Ocular Treatment-Emergent Adverse Events by System Organ Class and Preferred Term – Study Eye – SAF Population
14.3.2.4.1	Ocular Treatment-Emergent Adverse Events by System Organ Class and Preferred Term – Fellow Eye – SAF Population
14.3.2.4.2-4	Related Ocular Treatment-Emergent Adverse Events by System Organ Class and Preferred Term – Fellow Eye – SAF Population

Confidential

14.3.2.5.1	Non-Ocular Treatment-Emergent Adverse Events by System Organ Class and Preferred Term – SAF Population
14.3.2.5.2-4	Related Non-Ocular Treatment-Emergent Adverse Events by System Organ Class and Preferred Term – SAF Population
14.3.2.6.1	Treatment-Emergent Adverse Events by Worst Severity, by System Organ Class and Preferred Term- SAF Population
14.3.2.6.2	Ocular Treatment-Emergent Adverse Events by Worst Severity, by System Organ Class and Preferred Term – Study Eye – SAF Population
14.3.2.6.3-8	Related Ocular Treatment-Emergent Adverse Events by Worst Severity, by System Organ Class and Preferred Term – Study Eye – SAF Population
14.3.2.7.1-3	Related Non-Ocular Treatment-Emergent Adverse Events by Worst Severity, by System Organ Class and Preferred Term – SAF Population
14.3.3.1	Serious Adverse Events by System Organ Class and Preferred Term – SAF Population
14.3.3.2-4	Related Serious Adverse Events by System Organ Class and Preferred Term – SAF Population
14.3.3.5	Adverse Events Leading to Death by System Organ Class and Preferred Term – SAF Population
14.3.4.1	Hematology: Values and Changes from Baseline by Visit – SAF Population
14.3.4.2	Biochemistry: Values and Changes from Baseline by Visit – SAF Population
14.3.4.3	Hematology – Shift From Baseline NCI-CTC Grade To Worst Post-Baseline NCI-CTC Grade
14.3.4.4	Biochemistry – Shift From Baseline NCI-CTC Grade To Worst Post-Baseline NCI-CTC Grade
14.3.5.1	Vital Signs - Values and Change from Baseline by Visit – SAF Population
14.3.5.2	Summary of Intraocular Pressure (IOP) at each Visit – Study Eye - Safety Population
14.3.5.3	Summary of Intraocular Pressure (IOP) Increase on Treatment Days – Study Eye - Safety Population
14.3.6.1.1-8	Slit Lamp Biomicroscopy Exam: Descriptive Statistics (Frequencies) by Visit – Study Eye – SAF Population --- For Parameters: Motility, Lids/Lacrimal/Lashes, Conjunctiva/Sclera, Cornea, Iris, Pupils, Optic Nerve and Retina
14.3.6.2.1-4	Slit Lamp Biomicroscopy Exam: Descriptive Statistics (Frequencies) by Visit – Study Eye – SAF Population --- For Parameters: Anterior Chamber Activity , Vitreous Haze, Lens Status, Lens Status - Phakic
14.3.6.3.1-8	Slit Lamp Biomicroscopy Exam: Shift from Baseline to Week 12, 52 and 104 – Study Eye – SAF Population --- For Parameters: Motility, Lids/Lacrimal/Lashes, Conjunctiva/Sclera, Cornea, Iris, Pupils, Optic Nerve and Retina
14.3.6.4.1-3	Slit Lamp Biomicroscopy Exam: Shift from Baseline to Week 12, 52 and 104 – Study Eye – SAF Population --- For Parameters: Anterior Chamber Activity , Vitreous Haze, Lens Status
14.3.7.1	Fundoscopy Exam: Descriptive Statistics (Frequencies) by Visit – Study Eye – SAF Population
14.3.7.2	Fundoscopy Exam: Shift from Baseline to Week 12, 52 and 104 – Study Eye – SAF Population
14.3.7.3	Anti-Drug Antibodies: Descriptive Statistics (Frequencies) by Timepoint – SAF Population

